7 STATISTICAL ANALYSES

7.1 General Methods

The table below provides an overview of the efficacy analyses to be performed.

Table 1: Planned Efficacy Analyses

Measure of Interest (Primary and Secondary Efficacy Endpoints):	Analysis Method
Co-primary endpoints: ACR20 and 70 response rate at Day 85	Chi-Square test, two sided p-value will be provided. Point estimates and 95% CI of treatment difference.
Binary endpoints : ACR20, ACR50 and ACR70 response rate over time from baseline to Day 85; DAS28-CRP<2.6, DAS28-ESR<2.6, CDAI<=2.8, SDAI<=3.3 and Boolean remission over time from baseline to Day 85	Point estimate and 95% CI of response rate, point estimates and 95% CI of treatment difference.
Continuous endpoints: DAS28-CRP, DAS28-ESR, CDAI, SDAI, MRI scores (synovitis, osteitis, bone erosion and cartilage loss)	Mixed model analysis, point estimates and 95% CI for mean change from baseline within treatment groups, point estimates and 95% CI for mean change from baseline between treatment groups.

The Chi-square tests will be used to compare the ACR20 and ACR70 response rates at Day 85 between each of the active treatment arms and the placebo arm. The Chi-square p-value will be provided for each comparison between the active treatment and the placebo arm. Within each treatment group, the statistical testing will be performed for ACR20 at level of 0.05 first. If it is statistically significant, then the statistical testing will be performed for ACR70. Otherwise, testing will be stopped for this treatment group. All treatment groups will follow the same testing procedure. In addition, the difference of the response rates between each active treatment and the placebo will be estimated and their corresponding 95% confidence interval will be calculated. All subjects who discontinue prematurely during the treatment period or receive prohibited medications (refer to [Section 8.3](#)) will be counted as non-responder at subsequent visits.

For each of the binary endpoints, the estimate and its corresponding 95% confidence interval will be calculated for the difference of the proportions between each active treatment arm and the placebo arm at the specified visit, similar to the primary analysis except no p-values will be provided.

The construction of confidence intervals for binary variables will be based on normal approximation, if the number of the events in each individual treatment arm is at least 5. Otherwise, confidence interval using an exact method will be provided. The exact confidence intervals for binary variable within treatment group and between treatment groups will be constructed.

For each of the continuous endpoints, the mixed effect model will be fit with treatment and visit as the fixed effects and measurements within each subject as the repeated measurements. The baseline value will be added into the model as a covariate if necessary. Based on the mixed effect model, the estimate and 95% confidence interval will be calculated for the difference between each active treatment and the placebo at each specified visit.

The results will be presented by treatment groups unless otherwise specified.

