Study Summary: Subjects with moderate to severely active RA who have had an inadequate response to MTX with or without prior inadequate response to up to 2 TNF inhibitors will receive BMS-986142 or placebo daily for up to 12 weeks.

Upon meeting the Inclusion/Exclusion criteria, approximately 328 subjects will be randomized to 1 of the 4 treatment arms as shown in [Figure 1](#) below.

Interim analyses (IA) of clinical and PK data up to 12 weeks will be performed after approximately 20 subjects per treatment arm reach Week 4 (complete 4 weeks of treatment or discontinue) and complete the specified assessments for efficacy (ie, DAS28-CRP), safety, and PK. The purpose of this interim analysis is to adapt study design including dose, and sample size.

Subjects who were enrolled before the IA is completed will continue the originally assigned dose level if they have received at least 1 treatment and the dose is considered safe.

Figure 1: Study Design Schematic

Duration of Study:

Approximately 4 weeks for screening, 12 weeks of treatment, and 4 weeks of safety follow-up. Total duration for the study is approximately 20 weeks for the study and safety follow-up.

Number of Subjects:

About 328 subjects will need to be randomized for the 4 arms of this study. The study will utilize an equal randomization scheme that will result in approximately 82 subjects in each arm. Should the IA analysis for futility and dose adaptation suggest that an additional one or 2 dose levels be added, then up to 82 additional subjects per arm may be randomized for up to 408 total potential subjects and randomization ratio will be adjusted accordingly.

At this time, BMS (the Sponsor) has elected to stop recruitment to the study on November 30th 2017. The company regularly reviews its ongoing studies within development programs to determine acceptability of continuation due to changing business needs, benefit-risk and/or the desire to accelerate decisions to advance a program. The Sponsor want(s) to emphasize that the stopping of enrollment in this study, prior to recruiting the planned number of subjects is not related to any adverse events (AEs) associated with the use of BMS-986142.

Study Population:

Men or women (not nursing or pregnant) \geq 18 years of age with a diagnosis of RA by standard criteria at least 16 weeks prior to screening and who are inadequate responders to MTX with or without inadequate response to up to 2 TNF inhibitors.

Key Inclusion Criteria:

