- Change from baseline in RAMRIS Scores of synovitis, osteitis, bone erosion and cartilage loss to Week 4 and Week 12

The details of the analyses, endpoints and grouping schemes (treatment groups) will be provided in the statistical analysis plan (SAP).

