7.5.2 Secondary Efficacy Endpoints in Double-blind Period

For each of the binary endpoints (DAS28-CRP<2.6, CDAI<=2.8 etc.), the estimate and its corresponding 95% confidence interval will be calculated for the difference of the proportions

between each active treatment arm and the placebo arm for each applicable visit, similar to the primary analysis except no p-values will be provided.

For each of the continuous endpoints (DAS28-CRP, CDAI, etc.), the mixed effect model will be fit with treatment and visit as the fixed effects and measurements within each subject as the repeated measurements. The baseline value will be added into the model as a covariate if necessary. Based on the mixed effect model, the estimate and 95% confidence interval will be calculated for the difference between each active treatment and the placebo at each specified visit. No p-values will be provided. In addition, descriptive summary statistics of mean change from baseline and 95% confidence interval for each treatment arm will be provided. The missing data in continuous measures will be handled via utilization of mixed model procedure in SAS.

7.5.2.1 *Magnetic Resonance Imaging (MRI)*

Magnetic resonance imaging will be performed at baseline, Week 4 and Week 12 (or at the time of discontinuation, e.g., early termination visit [ET]). The independent read of MRI image data will be performed by two primary readers who have no knowledge of the subject's identity, treatment arm or time point chronologic sequence. The readers will be presented with the image set(s) of the most clinically swollen hand/wrist acquired at baseline and of that same hand/wrist acquired at Week 4 and Week 12 for the assessment of four parameters of bone erosion, bone marrow edema (osteitis), synovitis, and cartilage loss (joint space narrowing). The scoring of four parameters will be assessed according to the OMERACT RAMRIS criteria⁹.

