The MRI score for each parameter is the sum of scores at joints/bone ends where applicable by each reader. The MRI score that is used in the analyses is calculated as the average of MRI scores provided by the two readers for each parameter per each subject at each visit. If a MRI score from one of the readers is missing, then MRI score from the other reader will be used. If the score is missing for both readers at any given time point, the average score is considered missing. If a case requires adjudication, a consensus read of all four parameters will be performed by the two readers working together as defined in the charter. The consensus score will be used in the analysis in this case for each of the four parameters.

If there are more than 20% of joints/bone ends with missing score, the MRI score of each parameter will be considered missing. If there are less than or equal to 20% of joints/bone ends with missing score, the MRI score of each parameter from the missing joints/bone ends will be carried forward from previous scan (e.g., baseline to Week 4, Week 4 to Week 12), or carried backward from later time point or early termination visit (ET) scan if previous scan is not available (e.g., Week 12 to Week 4). If subjects had missing complete MRI assessment at Week 4 or 12, their assessment will be imputed via linear in/extrapolation. Imputation will require a subject to have available scores at minimum 2 visits (including baseline, Week 4, Week 12 or early termination (ET) visit). Subjects with no baseline or only baseline scores will be excluded from the analysis.

The following analyses will be performed based on imputed data unless specified otherwise. In addition, the analysis of changes from baseline may be performed based on as-observed data to assess the robustness of results at the presence of missing data.

The summary of changes from baseline to Week 4 and 12 in each of four parameters will be provided by treatment group using a mixed model. The proportion of subjects with new erosion count (defined as erosion score =0 at baseline and erosion score >0 at post baseline) per hand/wrist will be also summarized at Week 4 and 12.

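### The mixed model for the continuous secondary endpoints has no treatment-by-visit term, so it cannot give the visit-specific differences the plan asks of it

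*SAP*

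**What the plan says.** SAP 7.1 gives the model for continuous outcomes as follows: "the mixed effect model will be fit with treatment and visit as the fixed effects and measurements within each subject as the repeated measurements". It then requires from that model that "the estimate and 95% confidence interval will be calculated for the difference between each active treatment and the placebo at each specified visit". SAP 7.5.2 and Protocol 8.4.2 repeat both statements in almost the same words. On covariates, the text is: "The baseline value will be added into the model as a covariate if necessary". No rule is given for deciding when it is necessary.

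The model covers change in DAS28-CRP, DAS28-ESR, CDAI and SDAI. It also covers the MRI scores: the list in Protocol 8.4.2 includes "Change from baseline in RAMRIS Scores of synovitis, osteitis, bone erosion and cartilage loss to Week 4 and Week 12", and Table 1 of the SAP puts the MRI scores in the same row as the clinical scores. SAP 7.5.2.1 says only that the summary of changes "in each of four parameters will be provided by treatment group using a mixed model", without naming terms.

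Protocol 8.4.2 refers to the SAP for analysis details, but the SAP adds no further model terms. For binary and continuous secondary endpoints alike, SAP 7.5.2 says that "no p-values will be provided". SAP 8.5.2 relies on the repeated-measures analysis to handle missing continuous data under a missing-at-random assumption.

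**The concern.** A model with additive treatment and visit effects assumes that the treatment difference is the same at every visit. The plan asks that model for a separate difference at each visit. A programmer who follows the text would print one number and one interval against Weeks 2, 4, 8 and 12.

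If the effect builds up over the 12 weeks, that number understates the Week 12 difference and overstates the early ones. Nothing in the plan assumes a constant effect. The secondary objective asks for outcomes at Week 12 and over 12 weeks, and the interim analysis treats DAS28 at Week 4 and Week 12 separately. No tests are planned for these endpoints, so the estimates and intervals are the whole of the planned between-arm inference.

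**Working it through.** The plan states no figure for this model, so there is none to reproduce. The first step is algebra, and the rest is illustration under stated assumptions.

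**1. The contrast as written.** For arm i at visit j, the mean is

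E[Y] = μ + treatment_i + visit_j (+ β × baseline).

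The active-placebo contrast at visit j is treatment_active − treatment_placebo. It does not contain j. It is therefore the same at every visit under any within-subject covariance, with or without baseline.

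A REML fit to one simulated two-arm data set (82 per arm, four visits, true differences −0.2, −0.5, −0.8, −1.0) shows this:

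| Model | Wk 2 | Wk 4 | Wk 8 | Wk 12 |
|---|---|---|---|---|
| treatment + visit | −0.774 | −0.774 | −0.774 | −0.774 |
| treatment + visit + baseline | −0.787 | −0.787 | −0.787 | −0.787 |
| treatment × visit + baseline | −0.104 | −0.636 | −1.166 | −1.241 |

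**2. What the common value estimates.** With correlation matrix R, equal variances and complete data, the visit weights are w = R⁻¹1 / (1′R⁻¹1). The variance of the common difference is 2·SD² / (n·1′R⁻¹1).

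Under compound symmetry the four weights are equal. Take the true Week 12 improvement as 1.0 (assumed):

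- constant: (1 + 1 + 1 + 1)/4 = 1.00
- fast onset: (0.6 + 0.8 + 0.95 + 1.0)/4 = 0.84
- intermediate: (0.3 + 0.5 + 0.8 + 1.0)/4 = 0.65
- linear: (2/12 + 4/12 + 8/12 + 12/12)/4 = 0.54

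Across compound symmetry and AR(1) with correlation 0.3 to 0.7, the ratios to the true Week 12 difference are 1.00, 0.82–0.84, 0.65 and 0.54–0.56. They do not depend on the SD, on the sample size or on the size of the effect.

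MRI is measured after baseline only at Weeks 4 and 12, so the ratio is the mean of two values: 1.00, (0.8 + 1)/2 = 0.90, (0.5 + 1)/2 = 0.75 and (1/3 + 1)/2 = 0.67.

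**3. Precision.** Assume SD 1.2 and compound-symmetric correlation 0.5, with the planned 82 per arm.

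- Common difference: SE = √[(2 × 1.44/82) × (1 + 3 × 0.5)/4] = 0.148.
- Visit-specific difference: SE = √(2 × 1.44/82) = 0.187.

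**4. Coverage of the true Week 12 difference by the common 95% interval.** Let b be the common value minus the true Week 12 difference. Coverage = Φ(1.96 − b/SE) − Φ(−1.96 − b/SE). For intermediate onset, b = 0.65 − 1.0 = −0.35 and b/SE = −2.36, which gives 34%.

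| Assumptions (correlation 0.5) | Constant | Fast | Intermediate | Linear |
|---|---|---|---|---|
| Difference 1.0, SD 1.2, n = 82 | 95% | 81% | 34% | 13% |
| Difference 1.0, SD 1.0 to 1.5, n = 82 | 95% | 74–86% | 19–53% | 4–30% |
| Difference 1.0, SD 1.2, n = 40 | 95% | 88% | 62% | 42% |
| Difference 0.6, SD 1.2, n = 82 | 95% | 90% | 71% | 54% |
| Difference 0.4, SD 1.2, n = 82 | 95% | 93% | 84% | 76% |

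The values 1.0 and 0.6 are the DAS28 cutoffs used at the interim analysis. The row with 40 per arm is there because the Protocol Synopsis says enrollment stopped "prior to recruiting the planned number of subjects"; the bias is the same at any sample size. Across the other correlation structures (difference 1.0, SD 1.2, n = 82), linear-onset coverage runs from 3% to 21%.

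A check with 50,000 simulated sets of visit mean differences (first row of the table) gave common estimates of 0.999, 0.838, 0.650 and 0.541. Coverage was 95.0%, 80.7%, 34.5% and 12.6%, against 95% for the visit-specific contrast in every case.

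**The case against.** The strongest reply is that this is a gap in wording. A request for a difference at each visit makes sense only with an interaction, and naming treatment and visit may mean naming the factors, not listing every term. That may well be what the authors meant. But the same sentence stands in three places, nothing in either document corrects the literal reading, and the choice should not be left until after unblinding.

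Second, the consequence is limited. These are secondary endpoints without p-values, and no success criterion or dose-adaptation rule uses this model. That stands and limits the severity. It does not make a wrongly centred interval harmless when the interval is the only planned between-arm result.

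Third, SAP 7.5 plans results for continuous endpoints over time, and SAP 7.5.2 adds descriptive mean change with an interval for each arm. Shown by visit, which is the likely reading, these would expose a large mismatch at Week 12. They are not between-arm contrasts, however, and do not handle missing data as SAP 8.5.2 intends.

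Fourth, the coverage figures depend on the assumed effect size and are much milder at 0.6 or 0.4 than at 1.0. That is correct. The ratios are the better measure of the problem, because they do not depend on effect size.

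**Conclusion.** The concern holds. As written, the model cannot give the output required of it. It returns one covariance-weighted average difference for all visits, and this rests on algebra alone.

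The size of the error depends on the true time course, which the documents do not give. There is none if the effect is constant. Under the assumed onset patterns, with equal variances and complete data, the Week 12 difference is understated by about 16% to 46% for the clinical scores (ratios 0.84 down to 0.54) and by 10% to 33% for MRI (0.90 down to 0.67). The interval is also narrower than a visit-specific one.

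The co-primary chi-square tests, the binary secondary endpoints and the Bayesian interim rule are not affected. The point should be fixed, but it does not threaten the main conclusion of the trial.

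The undecided baseline covariate is a smaller, separate matter of pre-specification and precision. Under randomization it does not bias the contrast.

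**What to change.** In Protocol 8.4.2, SAP 7.1 and SAP 7.5.2, add the treatment-by-visit interaction to the fixed effects, and state that the Week 12 and other visit contrasts are taken from it. In SAP 7.5.2.1, state that the MRI scores use the same model with their own visits. Replace the conditional wording on baseline with a statement that the baseline value is always included.

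A baseline-by-visit term, a named covariance structure and the stratification factors as covariates could be considered at the same time, but they are not needed to correct this point.

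The cost is one added term in three places, a few degrees of freedom and no extra data. The visit-specific intervals are wider (SE 0.187 against 0.148 under the assumptions above) but correctly centred.

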7.2 Study Conduct

Relevant protocol deviations, which could have an impact on the primary/key efficacy endpoint, will be identified for all subjects who are randomized and receive study medication during the double-blind period. Details of relevant protocol deviations are provided in [Appendix 1](#).

All subjects with relevant protocol deviations that could affect the primary efficacy will be identified prior to database lock and unblinding of treatment assignment. All relevant protocol deviations will be listed and summarized by treatment group. The subjects identified as relevant protocol deviation will not be excluded from any analysis population described in [Section 6.3](#).

7.3 Study Population

Frequency distributions or summary statistics of data pertaining to subject disposition, demographic characteristics, baseline disease characteristics, and medical history will be tabulated and displayed by treatment group. No statistical test will be carried out for comparison of any baseline measures among treatment groups.

These presentations will be provided by randomized treatment group for the MITT analysis population unless specified otherwise.

7.3.1 Subject Disposition

The number of subjects enrolled into the study at screening, the number of subjects randomized, the number of subjects entering the double-blind period (DB) and the number of subjects who complete the double-blind period will be summarized by treatment group. The number of subjects discontinuing from the DB period (subject disposition) will also be summarized, together with the reasons for discontinuation, taken from the CRF status pages. The subject disposition for the DB period will be based on the MITT analysis population.

7.3.2 Demography and Baseline Characteristics

Demographic and baseline disease characteristics will be summarized by randomized treatment group and overall based on the MITT analysis populations. For continuous variables, they will be summarized using means, standard deviations and ranges. The distribution of categorical variables such as gender, race etc. will be summarized by treatment group using frequency and percentage.

Demographic characteristics include the following:

- Age in years
- Weight in kgs
- Gender: Male, Female

- Race
- Ethnicity (Hispanic and Non-Hispanic)
- Region grouping scheme A (Latin America+East Europe and ROW) [details in [Appendix 2](#)]
- Region grouping scheme B (North America, Latin America, Europe and ROW) [details in [Appendix 2](#)]
- Stratification (MTX-IR vs. TNF-IR)

Baseline clinical characteristics include the following:

- Duration of disease in years
- Duration of disease (<=2 years, > 2 to 5 years, > 5 years to 10 years, > 10 years)
- ACR functional status classification
- RA classification (2010 ACR/EULAR criteria)
- Individual scores of each ACR components
- DAS28-CRP
- DAS28-ESR
- RF Status: Negative versus Positive
- ACPA Status: Negative versus Positive
- hsCRP (mg/L)
- ESR (mm/hr)
- MTX weekly dose
- Oral daily steroid dose (prednisone equivalents) in mg at Day 1
- Prior non-biologics DMARD therapy: Categorized number of non-biologic DMARDs use prior to randomization (0, 1, 2, >=3)
- Number of subjects with inadequate and/or intolerance to TNFi (overall Yes/No, then categorized by intolerant, no response, insufficient response, and loss of response. Note: subject can be included in more than one category)
- Number of subjects with a primary failure (i.e., insufficient response to the first course of Therapy) (Yes, No)
- Number of subjects with TNFi failures: 0, 1, 2, or >2

7.3.3 *Medical History and Prior Medication*

Medical history and prior medication information before the first study medication will be summarized by treatment group using relative frequencies. Listings of medical history and prior medication will be presented. The results will be based on the MITT analysis population.

7.4 Extent of Exposure

7.4.1 Study Therapy

In general, extent of exposure will be summarized for the As-treated analysis population in two ways:

- by the number of study drug doses. Frequency distribution of number of doses will be summarized
- by the number of days the subject is known to be on study drug, ignoring any dosing interruptions

In general, exposure to study drug during the double-blind (DB) period in days is calculated as:

For subjects who discontinue study medication,

- Exposure = (date of last DB dose - date of first DB dose + 1) + 30.

The offset of 30 days represents 30 days of follow-up after last dose and is a lot longer than 5 times of half-life of the study medication. The frequency will be presented according to the duration ranges (in days) : <28, 29-56, 57-84 and so on.

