≥ 28 mm/hr on Screening Visit #1 for those not requiring washout of DMARDs and on Screening Visit #2 for those requiring washout.

- h) This study permits the re-enrollment of a subject that has discontinued the study as a pre-treatment failure (ie, subject has not been randomized / has not been treated). If re-enrolled, the subject must be re-consented and a new subject number obtained.

3. Age and Reproductive Status

- a) Males and Females, ages ≥ 18 years old, inclusive.
- b) Women of childbearing potential (WOCBP) must have a negative serum or urine pregnancy test (minimum sensitivity 25 IU/L or equivalent units of HCG) within 24 hours prior to the start of study drug.
- c) Women must not be breastfeeding
- d) WOCBP must agree to follow instructions for method(s) of contraception for the duration of treatment with BMS-986142 plus 90 days post-treatment completion or longer if required based on country specific guidelines for MTX use (please refer to MTX product label for details on your country specific guidelines).
- e) Male subjects must be willing to refrain from sperm donation during the entire study and for 5 half-lives of study drug plus 90 days (duration of sperm turnover) for a total of 93 days after dosing has been completed or longer if required based on country specific guidelines for MTX use (please refer to MTX product label for details on your country specific guidelines). Males who are sexually active with WOCBP must agree to follow instructions for method(s) of contraception for the duration of treatment with BMS-986142 plus 5 half-lives of BMS-986142 (~3 days) plus 90 days (duration of sperm turnover) for a total of 93 days post-treatment completion or longer if required based on country specific guidelines for MTX use (please refer to MTX product label for details on your country specific guidelines).
- f) Azoospermic males are exempt from contraceptive requirements. WOCBP who are continuously not heterosexually active are also exempt from contraceptive requirements, and still must undergo pregnancy testing as described in this section.
- g) Women/men who are not using hormonal contraceptives (oral, parenteral or implantable).

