6.3 Populations for Analyses

- All Enrolled Subjects: All subjects who sign an informed consent.
- All Randomized Subjects: All subjects who are randomized to a treatment.
- Modified Intent-to-Treat (MITT) Analysis Population: All randomized subject who have received at least one dose of the study medication. Subjects will be grouped according to the treatment to which they were randomized by IVRS at the start of the study. The MITT analysis population will also be referred to as “All Randomized and Treated Subjects”.
- As-Treated Analysis Population: All Subjects who have received at least one dose of study medication. Subjects will be grouped according to the treatment that they actually received as opposed to the treatment to which they were randomized. Subjects will be grouped on an as randomized basis unless the subject received the incorrect medication for the entire period of treatment. In that case, the subject will be analyzed in the treatment group associated with the incorrect medication he/she received.
- Efficacy Analysis Population: This is a subset of the MITT Analysis Population where the subjects who are randomized to a treatment arm and discontinued based on the interim analysis are excluded. All efficacy results involve statistical comparison or modeling will be based on this analysis population unless otherwise specified.
- [REDACTED]
- [REDACTED]
- Pharmacokinetic Population: All subjects who have received BMS-986142 and have any available concentration-time data.

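### SAP 7.4.1 adds 30 off-drug follow-up days to time on study drug for subjects who discontinue, so their reported exposure is 30 days too long and the under-28-day category is empty at the final analysis

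*SAP*

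**What the plan says.** SAP section 7.4.1 plans two summaries of exposure in the As-Treated population. One is a frequency distribution of the number of doses. The other is a duration, given "by the number of days the subject is known to be on study drug, ignoring any dosing interruptions".

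The duration formula is introduced with "For subjects who discontinue study medication" and reads "Exposure = (date of last DB dose - date of first DB dose + 1) + 30". The SAP then says what the added days are: "The offset of 30 days represents 30 days of follow-up after last dose and is a lot longer than 5 times of half-life". The results are to be tabulated in the categories "<28, 29-56, 57-84 and so on".

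No formula is stated for subjects who complete treatment. Section 7.4.2 defines discontinuation as stopping study medication for good before study completion, so a completer is not a discontinuer in the SAP's own terms.

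**The concern.** A follow-up day after the last dose is not a day known to be on drug, so the stated quantity and the formula cannot both be right. The categories are four-week blocks that fit a 12-week course of dosing. They do not fit dosing plus 30 days.

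At stake is whether the duration table in the study report shows time on drug. This is a dose-ranging trial, and exposure by arm is part of the context for reading the safety data. As written, subjects who stop early are moved into longer-duration categories, and an arm with more early stopping has more of its subjects moved. Because completers have no rule, two programmers could also produce different tables from the same data.

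**Working it through.** The plan states no exposure result, so there is no figure to reproduce. The check applies the formula to the possible durations.

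**Inputs**
- Formula, offset and categories: SAP 7.4.1, as quoted above.
- Minimum dosing: the As-Treated population in SAP 6.3 is "All Subjects who have received at least one dose of study medication", so the shortest time on drug is 1 day.
- Planned treatment: 12 weeks of daily dosing (SAP 2.1), or 84 days. The ±5-day visit window (Protocol Table 5.1-2) gives about 79 to 89 days for a completer.
- Elimination: Protocol 3.3.1 counts contraception as treatment "plus 5 half-lives of BMS-986142 (~3 days"), so five half-lives are about 3 days.

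**Step 1: could the offset be residual drug exposure?** 30 / 3 = 10. The offset is about ten times the five-half-life period, which agrees with the SAP's own remark. Nearly all of the 30 days are therefore off drug even on a generous reading.

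**Step 2: minimum value.** One dose means last date = first date, so (0 + 1) + 30 = 31. Nobody covered by the formula can fall below 28 days.

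**Step 3: apply the formula.** Reported value = days on drug + 30.

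| Days on drug | Category by days on drug | Reported days | Category reported |
|---|---|---|---|
| 1 | under 28 | 31 | 29-56 |
| 14 | under 28 | 44 | 29-56 |
| 26 | under 28 | 56 | 29-56 |
| 27 | under 28 | 57 | 57-84 |
| 28 | none | 58 | 57-84 |
| 54 | 29-56 | 84 | 57-84 |
| 55 | 29-56 | 85 | 85 or more |
| 60 | 57-84 | 90 | 85 or more |

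So 1-26 days on drug is reported as 29-56, 27-54 days as 57-84, and 55 days or more as 85 or more.

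**Step 4: completers.** There are two readings.
- With the offset: 84 + 30 = 114, and 114 / 84 = 1.36.
- Without it: a completer is reported as 84, while a discontinuer at 60 days is reported as 90. Any discontinuer with at least 55 days on drug (55 + 30 = 85) would outrank the 84-day completer.

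On either reading a completer has about 79 days or more and cannot enter the under-28 category. That category is therefore empty at the final analysis.

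**Step 5: remove the offset.** One dose gives 1 day and a full course gives 84. Durations of 1-27, 29-56 and 57-84 days then fall in their matching categories. Exactly 28 days still falls in none, because the first category stops below 28 and the second starts at 29.

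**The case against.** The best defence is that the 30 days are deliberate and disclosed. SAP 6.1 runs the double-blind period to 30 days after the last dose, sections 7.6 and 7.6.1 use the same window for adverse events, and the formula is introduced as exposure during that period. On this view it is a time-at-risk convention and not an arithmetic slip. That explains where the 30 came from, and it makes the defect a mismatch of label and categories with the formula. It does not reconcile the formula with a summary described as days on drug, or with categories whose first entry cannot be filled.

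Three stronger readings are tempting and are not supported:
- **That safety rates are distorted.** SAP 7.6.1 divides by the number of subjects dosed. The visible text plans no person-time or exposure-adjusted rate, so no planned adverse event percentage changes.
- **That early stopping is hidden.** It stays visible in the dose-count distribution (7.4.1), the disposition table (7.3.1) and the discontinuation summary by reason (7.4.2). The last two do not give time on drug, so they do not correct the duration table.
- **That every subject is inflated, with a full course overstated by 36%.** The formula is stated only for discontinuers. The 114-day figure needs the formula to be extended to completers, which the SAP does not say.

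The gap at 28 days is also minor. It catches nobody under the formula as written and matters only once the offset is removed.

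**Conclusion.** The point holds for subjects who discontinue. Each of their durations is reported 30 days longer than the on-drug time the SAP says it is summarizing, most move up one four-week category, and some (27, 55 and 56 days on drug) move up two. The under-28-day category is empty at the final analysis. This assumes only that the formula is applied as written to the As-Treated population. At the interim, subjects still on drug are not discontinuers, so the statement about the empty category is limited to the final summary.

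For completers the defect is a missing rule, and both ways of filling the gap misstate exposure: 114 days in place of 84, or a ranking in which some discontinuers exceed completers.

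The consequence is confined to one descriptive table. Efficacy tests and adverse event incidence are not affected. It should be corrected because the rule as stated gives a wrong result and correcting it is cheap.

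**What to change.** In SAP 7.4.1:
- Define on-drug exposure as date of last double-blind dose minus date of first double-blind dose plus 1, for all treated subjects, whether they complete or discontinue.
- Use the categories 1-28, 29-56, 57-84 and over 84 days. This also closes the gap at 28 days.
- If the 30-day extension is wanted, report it as a separate quantity labelled double-blind-period or adverse event observation time, with categories suited to its range.

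The cost is SAP wording and the matching table program. The dose dates are already used by the existing formula, so no new data are needed.
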